8.4.7. Overdose, Medication Errors, and Misuse

Overdose (defined as any dose administered or received that was higher than the intended dose), medication errors (defined as any unintentional error in the dispensing or administration of the study drug), and misuse of the study drug are considered reportable experiences. The method for completing and transmitting reports of these experiences are provided in [Appendix 4](#).

If any overdose, medication error, or misuse of the study drug results in an AE, this must be recorded. If the AE is serious, it must also be reported as described in [Appendix 4](#).

Decisions regarding dose interruptions or modifications will be made by the investigator in consultation with the Medical Monitor based on the clinical evaluation of the participant.

[REDACTED]

8.6. Genetics and/or Mutational Analyses

- In the HRD-positive malignancies agnostic cohort, blood and (optional) tumor samples may be tested to confirm pre-identified germline and/or somatic mutations.
- In all cohorts, blood may be tested for pathogenic somatic mutations in DNA and/or expression changes in RNA relevant to the mechanism of action of lurbinectedin and to evaluate and association with observed clinical response.
- [REDACTED]
- Samples may also be used for research to develop methods, assays, prognostics and/or companion diagnostics related to lurbinectedin.

- See [Appendix 6](#) for information regarding genetic research. Details on processes for collection and storage and destruction of these samples can be found in the laboratory manual.

8.6.1. Required Analyses

The following samples will be collected for analysis before lurbinectedin administration in Cycle 1:

- **Homologous recombination deficient-positive malignancies agnostic cohort:**
 - Blood for confirmation of any pre-identified germline and/or somatic pathogenic mutations.
 - Blood for longitudinal mutational analysis.
- **All cohorts:**
 - Baseline blood for mutational analysis.

[REDACTED]

8.8. Immunogenicity Assessments

Immunogenicity parameters are not evaluated in this study.

8.9. Health Economics

Health economics parameters are not evaluated in this study.

9. STATISTICAL CONSIDERATIONS

9.1. Statistical Hypotheses

This nonrandomized multi-cohort signal finding study will use estimation rather than hypothesis testing to characterize the ORR for each cohort.

9.2. Sample Size Determination

This study is designed to assess the antitumor activity of lurbinectedin in terms of the ORR according to the RECIST v1.1 in 3 different advanced (metastatic and/or unresectable) solid tumors cohorts. This study includes up to a total of 60 participants in the initial assessment of efficacy in which each tumor cohort includes up to 20 participants. If there is evidence of efficacy, enrollment beyond 20 participants in the individual cohort may be considered.

Each cohort will have up to 4 stages: stage 1 at n = 12 and stage 2 at n = 20 for futility testing (see [Section 9.5](#)); if a cohort enrolls beyond 20 participants, the study may enroll stage 3 with an interim analysis to assess efficacy at n = 35, and a final stage 4 at n = 100 for the final analysis. If there are ≥ 4 responses (a target of 20% ORR) out of 20 participants in a cohort, the lower bound of 70% CI of ORR (10.5% to 33.4%) will exclude a 10% ORR (Table 7) and the cohort may continue. This will provide approximately 85% confidence that the true ORR rate is $> 10\%$, where a 10% or lower response rate is not clinically meaningful. If there are ≥ 8 responses (22.9% ORR) out of 35 participants in a cohort, the lower bound of 95% CI of ORR (10.4% to 40.1%) will exclude a 10% ORR (Table 8) and the cohort may continue enrollment up to a total of 100 participants. If there are ≥ 20 responses (20% ORR) out of 100 participants in a cohort, the lower bound of 95% CI of ORR (12.7% to 29.2%) will exclude a 10% ORR (Table 8).

Table 7: Two-sided, Exact CI of ORR Under Varying Scenarios for n = 20

Sample Size	No of Responders	Observed ORR (%)	70% CI of ORR (%)	80% CI of ORR (%)	90% CI of ORR (%)	95% CI of ORR (%)
	4	20	(10.5, 33.4)	(9.0, 36.1)	(7.1, 40.1)	(5.7, 43.7)
	5	25	(14.4, 38.8)	(12.7, 41.5)	(10.4, 45.6)	(8.7, 49.1)
	6	30	(18.5, 44.0)	(16.6, 46.7)	(14.0, 50.8)	(11.9, 54.3)
	7	35	(22.8, 49.1)	(20.7, 51.8)	(17.7, 55.8)	(15.4, 59.2)
	8	40	(27.2, 54.1)	(24.9, 56.7)	(21.7, 60.6)	(19.1, 63.9)

Abbreviations: CI = confidence interval; ORR = objective response rate.

Table 8: Two-sided, Exact CI of ORR Under Varying Scenarios for n = 35 and n = 100

Sample Size	No of Responders	Observed ORR (%)	95% CI of ORR (%)
35	7	20.0	(8.4, 36.9)
	8	22.9	(10.4, 40.1)
	9	25.7	(12.5, 43.3)
100	18	18.0	(11.0, 26.9)
	19	19.0	(11.8, 28.1)
	20	20.0	(12.7, 29.2)

Abbreviations: CI = confidence interval; ORR = objective response rate.

9.3. Analysis Sets

Participant Analysis Set	Description
Enrolled	All participants who sign the informed consent form
Safety	All participants who take at least 1 dose of study treatment. This is the primary set for safety analyses
Efficacy-evaluable	Participants in the Safety analysis set with measurable disease at baseline and one of the following: (a) at least 1 post-baseline evaluable tumor assessment, (b) clinical progression, or (c) death
[REDACTED]	[REDACTED]
[REDACTED]	[REDACTED]

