9.4.1.3. Dropouts and Missing Data

9.4.1.3.1. Imputation of Non-date Missing Data

Data used for evaluating efficacy and safety endpoints may be missing for technical reasons (eg, unreadable scan, participant missed appointment).

The primary efficacy analysis will be performed on the Efficacy-evaluable analysis set in this study. For participants without any post baseline disease assessment, the response of this participant will be imputed as non-responder for sensitivity analyses of ORR in the Safety analysis set.

Participants with the designation of treatment relationship for AEs and SAEs missing will have the worst case assumed to impute the relationship: if relationship to study treatment is missing it will be assumed to be “Yes.”

The details of analyses with missing data will be specified in the SAP.

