9.5. Interim Analysis

Review of the safety and efficacy data will be performed by the sponsor on an ongoing basis in this study. Assessment of the observed responses will be performed after enrollment of approximately 12 and 20 efficacy-evaluable participants for treatment benefit. If no confirmed response per RECIST v1.1 is observed in approximately the first 12 evaluable participants of a cohort, the recruitment of participants in that cohort will be stopped. If there are ≤ 3 confirmed responses in the first 20 evaluable participants of a cohort, the recruitment of participants in the cohort will be stopped. There will be no pause in enrollment during the interim analysis of the first 12 evaluable participants of a cohort, and the futility boundary will be adjusted based on the actual number of participants at each stage.

Interim futility monitoring will be implemented through the BPP approach with the prior distribution for ORR assumed to be Beta (0.5, 0.5). Table 10 has the operating characteristics for futility of stopping at 12 and 20 participants. If no response is observed in the first 12 participants of a cohort, there is an 89% posterior probability that the actual response rate is

no more than 10%. If there are ≤ 3 responses in the first 20 participants of a cohort, there is a 70% posterior probability that the actual response rate is no more than 20%.

Table 10: Posterior Probability for Interim Futility Monitoring

No Participants	Futility Stopping	Prob ($\theta \leq 10\% r, n$)	Prob ($\theta \leq 15\% r, n$)	Prob ($\theta \leq 20\% r, n$)
12	0	89%	95%	98%
20	1	76%	91%	97%
20	2	46%	72%	87%
20	3	21%	47%	70%

θ = True response rate; r = the observed responses; n = the number of participants

The SAP will describe the planned interim analyses in greater detail.

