## 6. ANALYSIS SETS

For purposes of analysis, the following populations are defined:

Analysis Set	Description
Enrolled	All participants who sign the informed consent form (ICF).
Safety	All participants who took at least one dose of study treatment. This is the primary set for safety analyses.
Efficacy evaluable	Participants in Safety analysis set with measurable disease at baseline and one of the following: (a) at least one post-baseline evaluable tumor assessment, (b) clinical progressions, or (c) death.
[REDACTED]	[REDACTED]
[REDACTED]	[REDACTED]

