#### 7.4.2. Imputation of Non-date Missing Data

Data used for evaluating efficacy and safety endpoints may be missing for technical reasons (e.g., unreadable scan, participant missed appointment).

The primary efficacy analysis for ORR will be performed on the Efficacy-evaluable analysis set.

Jazz Pharmaceuticals, Inc.

JZP712-201 Statistical Analysis Plan - Protocol Amendment

2

For participants without any post baseline disease assessment, the response will be imputed as non-responder for sensitivity analyses of ORR in the Safety analysis set.

AEs and SAEs with missing relationship to study treatment will be considered related to study treatment for the purpose of analyses.

AEs and SAEs with missing severity (CTCAE grade) will be considered missing for the purpose of analyses.

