### **9.1. Primary Efficacy Endpoint and Analysis**

#### **9.1.1. Primary Analysis**

The primary efficacy endpoint is the objective response rate (ORR).

Best overall response (BOR) is defined as the best response recorded between the date of the first dose of study treatment and the date of objectively documented progression per RECIST v1.1, or the date of subsequent anticancer therapy, death due to any cause, loss to follow-up, or study discontinuation, whichever occurs first. Best overall response (BOR) will be determined programmatically in the analysis of the study results as the best timepoint response that a participant achieves during the study (recorded between the date of the first dose of study treatment and the date of objectively documented progression per RECIST v1.1), with the

Jazz Pharmaceuticals, Inc.

JZP712-201 Statistical Analysis Plan - Protocol Amendment

2

response ranked according to the following order (from best to worst): complete response (CR) > partial response (PR) > stable disease (SD) > progressive disease (PD).

The first post-baseline tumor imaging assessment should occur 6 weeks (+/- 7 days) from the first dosing date. A response of SD can only be made after the participant is on-study for a minimum of 35 days from the date of the first dose. The number and percentage of participants in each category of BOR (CR, PR, SD, PD, not evaluable [NE]) will be presented by each cohort.

The ORR is defined as the proportion of participants whose BOR is investigator-assessed confirmed CR or PR using the RECIST v1.1. The ORR will be summarized by a binomial response rate for each cohort and its corresponding two-sided 95% exact CIs using the Clopper and Pearson method ([Clopper 1934](#)).

The calculation of the ORR and its corresponding two-sided 95% exact CIs will be carried out using the PROC FREQ procedure with the exact binomial option in SAS version 9.4.

A by-participant listing of best overall response will be presented by each cohort including best overall response and dates of CR/PR/progression.

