### **9.1.2. Sensitivity Analyses**

Not applicable.

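### The primary ORR leaves out dosed participants who are never scanned, have no clinical progression and are alive, and adds them as non-responders if a death is recorded later, so the denominator depends on post-baseline events and on the data cut.

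*Protocol*

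**What the plan says.** Protocol 9.3 admits a dosed participant with measurable disease at baseline to the Efficacy-evaluable set by one of three routes: "a) at least 1 post-baseline evaluable tumor assessment, (b) clinical progression, or (c) death". SAP 6 gives the same routes: "a) at least one post-baseline evaluable tumor assessment, (b) clinical progressions, or (c) death". Neither document puts a time window on route (b) or route (c).

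This set carries the main result. Protocol 9.4.1.3.1 states: "The primary efficacy analysis will be performed on the Efficacy-evaluable analysis set in this study". It also defines the n = 20 futility count: Protocol 9.5 stops recruitment at three or fewer "confirmed responses in the first 20 evaluable participants of a cohort". SAP 9.1.1 reports best overall response as "CR, PR, SD, PD, not evaluable [NE"], so someone who enters the set without a scan stays in the denominator and cannot be a responder.

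An all-dosed ORR appears only as a sensitivity analysis. For participants with no post-baseline disease assessment, Protocol 9.4.1.3.1 says "the response of this participant will be imputed as non-responder for sensitivity analyses of ORR in the Safety analysis set", and SAP 7.4.2 repeats it: "the response will be imputed as non-responder for sensitivity analyses of ORR in the Safety analysis set". SAP 9.1.2, which covers sensitivity analyses of the primary endpoint, reads "Not applicable".

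Deaths are sought by telephone every 3 months after the EOT visit, until at least 80% of each cohort have died, withdrawn or been lost (Protocol 4.1 and 4.4).

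**The concern.** Membership of the primary set is decided by what happens after dosing. A participant who received the drug and left before any evaluable scan has not been shown to respond. Such a participant counts against the drug if clinically progressed or dead, and is not counted at all if alive without clinical progression.

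Three consequences follow.

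- The excluded participants have no confirmed CR or PR, so leaving them out can only raise the ORR.
- Because Protocol 9.5 counts evaluable participants, the next evaluable participant takes the place of each one excluded.
- A later recorded death adds a non-responder, so the same responders can give a lower ORR at a later data cut.

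The result at stake is the primary endpoint of a single-arm study in which a cohort that meets the threshold may be expanded towards 100 participants and taken to regulatory discussion (Protocol 4.2 and 9.2).

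**Working it through.** **The plan's own figures.** The Clopper-Pearson lower limit is the α/2 quantile of Beta(r, n − r + 1), where 1 − α is the confidence level. It gives:

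- 4/20, 70% interval: 10.46% (Protocol Table 7: 10.5%)
- 8/35, 95% interval: 10.42% (Table 8: 10.4%)
- 20/100, 95% interval: 12.67% (Table 8: 12.7%)

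All three reproduce. The question is who belongs in n.

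**Who is affected, route by route.**

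1. Stops early with clinical progression: counted while alive by route (b).
2. Stops for toxicity or another reason that leaves the participant in the study: due a scan at the EOT visit (Protocol 7.1), so normally counted by route (a).
3. Starts another therapy: the EOT visit is to take place immediately before it (Schedule of Activities), so a scan is due there too.
4. Withdraws consent or is lost: the post-discontinuation scan provision in Protocol 7.1 does not cover these participants. They are excluded, often for good, because SAP 7.2.2 ends survival follow-up at withdrawal or loss.
5. Misses the EOT scan but stays in telephone follow-up: excluded while alive, and enters as a non-responder at any recorded death.

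Groups 4 and 5 make up the gap. Group 5 is the main source of change between data cuts.

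**Effect on the observed ORR.** With 4 responders among 20 dosed, leaving out k gives 4/(20 − k):

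- k = 0: 20.0%
- k = 1: 4/19 = 21.1%
- k = 2: 4/18 = 22.2%

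**Effect on the n = 20 rule.** Let p be the true ORR among all dosed, and let a fraction f be excluded, none of them responders. The ORR among evaluable participants is then p/(1 − f). The documents do not give f; 5% and 10% are assumptions. Take p = 10%, the rate Protocol 9.2 calls not clinically meaningful, and let X be Binomial(20, p/(1 − f)):

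| f | ORR among evaluable | P(X ≥ 4) |
|---|---|---|
| 0 | 10.0% | 13.3% |
| 5% | 0.10/0.95 = 10.5% | 15.2% |
| 10% | 0.10/0.90 = 11.1% | 17.5% |

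This treats the n = 20 rule alone and ignores the earlier stop at n = 12.

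**Sensitivity of the stated bounds.** Adding k excluded participants back as non-responders:

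| Criterion | k | ORR | Lower bound |
|---|---|---|---|
| 4/20, 70% | 1 | 4/21 = 19.0% | 9.95% |
| 8/35, 95% | 1 | 8/36 = 22.2% | 10.12% |
| 8/35, 95% | 2 | 8/37 = 21.6% | 9.83% |
| 20/100, 95% | 25 | 20/125 = 16.0% | 10.06% |
| 20/100, 95% | 30 | 20/130 = 15.4% | 9.66% |

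The margin over 10% is thin at n = 20 and n = 35 and wide at n = 100.

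**The case against.** The best defence is that the gap is small and largely planned for. Clinical progressors are counted, an EOT scan is due for most others who stop early, and SAP 8.3 lists failure to complete efficacy assessments as an important deviation subtype. The study is for signal-seeking and estimation, and expansion is at the sponsor's discretion. A late death lowers the ORR, so that part of the drift is conservative. The all-dosed ORR is already written down as a sensitivity analysis.

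Much of this stands, and it rules out two stronger readings.

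- A reader might infer that anyone who stops before a first scan is left out while alive. Route (b) and the EOT scan contradict that. In particular, a participant who switches therapy at Week 3 is due a scan before the switch.
- A reader might infer from 4/21 or 8/37 that a go decision would be reversed. The n = 20 rule in Protocol 9.5 is a count of responders among 20 evaluable participants, and its boundary is to be adjusted to the actual number at each stage. The bounds in Protocol 9.2 explain the thresholds; 4/21 and 8/37 are not decision points. They show only how thin the margin is.

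The n = 12 look also needs separate treatment. SAP 5.5 limits it to participants with two or more evaluable post-baseline assessments, so on that text a death without scans does not qualify anyone for that count. Protocol 9.5 has no such condition.

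The defence does not remove the selection on post-baseline events. Adjusting the boundary to the number evaluable does not restore those excluded. The sensitivity analysis enters no decision rule, and SAP 9.1.2 contradicts it.

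**Conclusion.** The point holds for a limited group: dosed participants with measurable disease, no evaluable post-baseline scan and no clinical progression. They are outside the primary ORR and the n = 20 count while alive, and enter as non-responders on a recorded death at any date. For a given set of responders the exclusion can only raise the ORR.

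The size is modest. At a true all-dosed ORR of 10%, the chance of passing the n = 20 rule rises by about 2 percentage points if 5% are excluded and about 4 if 10% are. Both rates are assumptions; the documents give no rate of leaving without a scan, and if nobody is affected the effect is nil. The 20/100 criterion still excludes 10% with 25 non-responders added. The change is worth making because it needs no new data and removes dependence on the data cut. The documents do not show that a cohort decision would be wrong.

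**What to change.** 1. In Protocol 9.3 and SAP 6, define the primary efficacy set as all dosed participants with measurable disease at baseline. Count anyone without an evaluable post-baseline assessment as a non-responder.
2. Use this set, in order of first dose, for the stage counts, once each participant has had the opportunity for response confirmation.
3. Keep the present evaluable set as a supportive analysis, with a fixed time window on routes (b) and (c).
4. Reconcile SAP 9.1.2 with SAP 7.4.2 and Protocol 9.4.1.3.1.
5. Reconcile the n = 12 population in SAP 5.5 with Protocol 9.5.

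The cost is matching edits wherever the set is used (Protocol 9.4.1.2, 9.4.1.3.1 and 9.5; SAP 5.5, 7.1, 7.4.2 and 9) and a slightly lower reported ORR. No extra data are needed.

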9.4. Statistical Analyses

The SAP will be finalized prior to DBL, and it will include a more technical and detailed description of the statistical analyses described in this section. This section is a summary of the planned statistical analyses of the most important endpoints, including primary and key secondary endpoints.

The primary analysis is planned to take place when the last enrolled participant in a cohort has had 6 months of treatment and follow up. The primary analysis may be performed separately for each cohort based on enrollment.

9.4.1. General Considerations

9.4.1.1. Definition of Study Periods for Analysis

9.4.1.1.1. Baseline

Baseline evaluations (eg, disease assessments, laboratory tests, vital signs, and ECOG performance status) will be defined as evaluations with a date on or prior to the date of first dose of study intervention. If there are multiple valid observations in the Screening Period, then the latest non-missing observation on or before the first dose of study intervention will be used as the baseline in the analyses.

Detailed instructions for assigning baseline values will be given in the SAP.

9.4.1.1.2. Post-baseline

Post baseline evaluations will be defined as evaluations taken after the date of the first dose of study treatment.

The post-baseline period is further characterized into a treatment period, a 30-day safety follow-up period after the last dose of study treatment, and an OS Follow-up Period.

Treatment-emergent adverse events are defined as AEs with an onset date on or after the date of the first dose of study treatment. An AE is a TEAE if it occurs up to 30 days after the last dose of study intervention. TEAEs can be pre-treatment AEs that worsen in CTCAE grade after the start of study treatment.

9.4.1.2. Statistical Methods

The efficacy analyses will be performed on the Efficacy-evaluable analysis set, separately for each cohort. The safety analyses will be performed on the Safety analysis set.

Unless otherwise noted, discrete measurements will be tabulated by the frequency and proportion of participants falling into each category within each cohort. Continuous measurements will be summarized using the sample size, mean, standard deviation, median, minimum, and maximum values for each cohort.

Time-to-event measurements will be summarized using K-M estimates. This will be done for the following endpoints: TTR, DOR, PFS, and OS. The TTR will also be analyzed using summary statistics such as mean, standard deviation, median, minimum, and maximum values. Median survival time will be reported along with 95% CIs constructed based on a log-log transformed CI for the survivor function (Brookmeyer, 1982). Rates at fixed times (3, 6, 9, and 12 months) will be derived from the K-M estimates if the data allow, and the corresponding CIs will be calculated based on Greenwood formula for variance derivation and on a log-log transformation applied to the survivor function (Greenwood, 1926; Kalbfleisch, 1980).

9.4.1.3. Dropouts and Missing Data

9.4.1.3.1. Imputation of Non-date Missing Data

Data used for evaluating efficacy and safety endpoints may be missing for technical reasons (eg, unreadable scan, participant missed appointment).

The primary efficacy analysis will be performed on the Efficacy-evaluable analysis set in this study. For participants without any post baseline disease assessment, the response of this participant will be imputed as non-responder for sensitivity analyses of ORR in the Safety analysis set.

Participants with the designation of treatment relationship for AEs and SAEs missing will have the worst case assumed to impute the relationship: if relationship to study treatment is missing it will be assumed to be “Yes.”

The details of analyses with missing data will be specified in the SAP.

